7.8. Development of a Medical Device

The long-term ambition of CoCoA-PAD is to validate the cognitive assessments and then work towards achieving NICE registration as a tier 3 digital health technology to 'inform clinical management'. Subsequent research will therefore require MHRA approval.

Having reviewed the UKMDR2002 flowchart for MHRA approval ([flowchart Cls - Studies under UKMDR2002 v1 A4.pdf](#)), this study does not require MHRA approval for the following reasons:

- All the CoCoA-PAD cognitive tests are novel and have not been previously validated. Therefore, the CoCoA-PAD assessment battery is currently experimental.
- Depending on the results of this study, the CoCoA-PAD assessment will be altered, i.e., insensitive tests will be removed from the assessment to reduce time. Therefore, the assessment battery is not yet finalised.
- The CoCoA-PAD tests are not being used for a medical purpose in this study. Participants' results will not be used for classification purposes, and participants will not receive any feedback on the CoCoA-PAD performance, because this data is currently uninterpretable.
- The data from the CoCoA-PAD tests are not being used to develop another medical device.

7.9. Commercialisation Strategy and Conflict of Interest

The long-term aim of the CoCoA-PAD project is to progress from a research-only tool to a validated, regulated digital health technology that can be implemented in NHS memory services. Intellectual property (IP) for the CoCoA-PAD assessment and associated training materials is owned by the University of Plymouth. Intellectual property (IP) for the speech biomarkers and associated training materials is owned by the University of Birmingham.

On the proviso that the CoCoA-PAD achieves diagnostic accuracy to reliably detect early AD related cognitive difficulties, the CoCoA-PAD team and University of Plymouth will pursue a non-profit commercialisation strategy to implement this tool into NHS clinical practice. This will involve seeking funding to recode the assessments into an app, so that they are compliant with Digital Technology Assessment Criteria (DTAC), applying for MHRA medical device registration, and completing subsequent large scale research validation (which will include groups excluded from this study, i.e., individuals with drug or alcohol dependency or English as a second language).

As the IP owner, the University of Plymouth may receive a proportion of any revenue generated from future licensing or deployment of CoCoA-PAD. The exact terms and percentage of this revenue share will be negotiated after the research phase, in accordance with the University's intellectual property policy and sector-standard commercialisation processes. At present, CoCoA-PAD is an experimental research tool, not a CE/UKCA-marked medical device, and there is no commercial sale or licensing during the study. The data collected will be used solely for research and development purposes, and participants will not receive any clinical diagnosis or treatment recommendations from the tool.

All members of the research team are either University or NHS employees with no personal financial stake in the commercialisation of CoCoA-PAD. Should any member of the research team acquire a personal interest in future commercial activity, this will be declared to the Sponsor, documented in the site file, and managed in accordance with University of Plymouth and NHS conflict-of-interest policies.

8. Study Management

8.1. Chief Investigator and Oversight

The Chief Investigator (CI) for the CoCoA-PAD study is [name], Doctoral Clinical and Practitioner Academic Fellow and Neuropsychology lab lead at the Brain Research and Imaging Centre at the University of Plymouth and Honorary Principal Clinical Neuropsychologist at University Hospitals Plymouth NHS Trust and Livewell Southwest. [name] holds a Doctorate in Clinical Psychology and postdoctoral training in Neuropsychology. He has eight years of experience in clinical neuropsychology and is listed on the British Psychological Society's Specialist Register of Clinical Neuropsychologists, representing the gold standard for professional competence in the field. [name] has overall responsibility for all aspects of the study, including adherence to the study protocol, participant safety, data integrity, and the

reporting of adverse events. He is funded by the National Institute for Health Research (NIHR) from June 2025 to September 2028 to deliver this project.

8.3. Trial Management Group (TMG)

The Trial Management Group will meet monthly. This meeting will be attended by:

- [name], Chief Investigator
- Members of the research team at University Hospitals Plymouth NHS Trust (UHP)
- Site representatives from North East London NHS Foundation Trust (NELFT) and Devon Partnership NHS Trust (DPT) sites
- A representative from the research sponsor, University of Plymouth

These meetings will provide structured opportunities to review recruitment progress, adverse events, protocol deviations, and upcoming amendments to the study design or documentation. The minutes of the monthly TMG meeting will be distributed to the research team and stored on the site file. This will facilitate an audit trail of decision making and research governance.

8.4. Project Steering Group / Advisory Group

A Project Steering Group will meet twice a year and will provide additional oversight. The group will include members from the project team, including:

- A PPI representative from the project coproduction group.
- Sponsor representative from University of Plymouth
- [name], Co-Investigator, Associate Professor in Dementia Research, University of Plymouth
- [name], Collaborator, Professor in Human Neuroimaging, University of Plymouth
- [name], Collaborator, Associate Professor in Psychology, University of Plymouth
- [name], Collaborator, Consultant Neuropsychologist, University Hospitals Plymouth NHS Trust

This group will review overall study performance against project targets, oversee any serious incidents or emerging risks, and serve as a forum for maintaining the ethical and scientific integrity of the study.

8.5. Sponsor and R&D Oversight

The study sponsor is University of Plymouth (UoP). Governance oversight will be supported by the Trial Management Team. The sponsor will ensure that the Site File is maintained to GCP standards and that monitoring and auditing activities are conducted across research sites. The sponsor will ensure the study complies with ethical standards.

8.6. Training and Protocol Compliance

All study personnel will be trained in Good Clinical Practice (GCP) and safeguarding protocols. The training requirements differ for different aspects of this study, so will be reported separately.

Blood Tests

All blood tests will be completed by NHS clinical research teams, as outlined in the Schedule of Events Cost Attribution Tool (SoECAT). Responsibility for training and oversight therefore sits with the local clinical research team, and their NHS trust. Only suitably qualified NHS Clinical Research Nurses and phlebotomists, who have experience working with older adults, will collect this data. Any deviations to the protocol or AEs will be recorded by the clinical professional.

MRI Scans

The MRI scans will be completed by an experienced radiographer at the Brain Research and Imaging Centre (BRIC), University of Plymouth. BRIC radiographers are employed by University Hospitals Plymouth NHS Trust and are therefore subject to NHS clinical training and governance standards. Their role involves providing clinical radiography services on 3 days per week, and research radiography services 2 days a week. As such, they have significant experience performing MRI imaging for older adults and people with significant cognitive difficulties. [name], lead radiographer, will oversee all MRI imaging activities.

Any staff involved in MRI activity, including being present at the time of the scan, are required to complete training on MRI safety

(<https://brichandbook.readthedocs.io/en/latest/mri.html#safety>).

Neuropsychological Assessment

[name] will administer the neuropsychological assessments to all Plymouth based participants and will provide full training to clinical research professionals at the two additional research sites: Devon Partnership NHS Trust and North East London NHS Foundation Trust. Professionals from both sites will receive training and 'sign off' before they are deemed eligible to deliver the assessment. Training and 'sign off' will be captured on the delegation log in the site file.

8.7. Training and Delegation Log

Training Procedures

All members of the CoCoA-PAD research team will receive study specific training before undertaking any delegated tasks. This will include:

- An overview of the study design, objectives, and procedures.
- Detailed instruction in participant recruitment, consent, capacity assessment, cognitive testing, MRI scanning, blood sampling, and data entry.
- Review of Good Clinical Practice (GCP) principles, the Mental Capacity Act (2005), data protection, and safeguarding.
- Familiarisation with the study's standard operating procedures (SOPs) and REDCap data management system.

Training will be delivered by the Chief Investigator (CI) or delegated senior research staff. Completion of training will be documented in REDCap, with an electronic signature and date for each staff member. This record will be available for monitoring and audit.

Delegation Log

A delegation log will be maintained electronically in REDCap for each research site. This will record:

- Staff member's name, job title, and site affiliation.
- GCP training completion date.
- Date of study specific training.
- Specific delegated tasks (e.g., obtaining consent, capacity assessments, administering cognitive tests, collecting blood samples, MRI scanning, data entry, adverse event reporting).
- PI signature and date confirming delegation.
- Staff signature and date confirming acceptance of delegated tasks.

Only staff listed and signed off on the delegation log will be permitted to carry out the tasks assigned to them.

PI and CI Responsibilities

The Principal Investigator (PI) at each site will:

- Ensure only qualified staff are delegated study duties.

- Verify that staff have current GCP certification and have completed study-specific training.
- Sign the delegation log to confirm delegation of tasks.
- Review and update the delegation log promptly if staff roles change.

The Chief Investigator (CI) will:

- Oversee delegation log maintenance across all sites.
- Ensure that training is consistent across sites.
- Monitor compliance with training and delegation requirements.

Data Security

The REDCap system will be hosted on secure University of Plymouth servers, meeting GDPR standards. Access to the training and delegation log will be access controlled, restricted to authorised study team members.

- All activity in REDCap is audit-trailed.
- Logs will be stored for the duration of the study and archived in line with sponsor policy.
- No delegation or training records will be shared outside the research team except for sponsor monitoring, audit, or regulatory inspection

8.8. Monitoring and Reporting

Internal monitoring will occur at least once per year. Additional audits will be triggered in response to serious adverse events, breaches of protocol, or concerns regarding data management. [name] will conduct routine audits in parallel with sponsor-led oversight.

Serious adverse events (SAEs) will be reported in accordance with established Good Clinical Practice (GCP) standards and UK research governance frameworks. All SAEs will be reported to the study sponsor, University of Plymouth, within 24 hours of the research team becoming aware of the event. This immediate notification will include a detailed description of the event, an initial assessment of seriousness, expectedness, and relatedness to the study procedures, and any actions taken in response. The sponsor will be responsible for assessing whether the SAE meets the criteria for onward reporting. In accordance with Health Research Authority (HRA) guidance, only SAEs that are both related to study procedures and unexpected—classified as Related and Unexpected Serious Adverse Events (RUSAEs) in non-CTIMP studies—will be reported to the Research Ethics Committee (REC). These events will be reported without delay and within a maximum of 15 calendar days from when the sponsor is made aware. All SAEs will be documented in the study's adverse event log and reviewed at regular Trial

Management Group meetings, with findings used to inform any necessary amendments to study procedures or participant-facing materials.

8.9. Insurance and Liability

This research is sponsored by the University of Plymouth, which has appropriate insurance in place (including public liability and professional indemnity) to provide cover for negligent harm arising from the management and design of the study. Where the research is conducted within the NHS, NHS indemnity will apply for clinical treatment and care provided to participants by NHS staff in the course of their normal duties. There are no arrangements for non-negligent harm indemnity in this study.

8.10. Timeline and Milestones

The CoCoA-PAD project timelines and milestones are outlined in Table 5. The progress of this research study will be reviewed against these targets are each project steering group to ensure the project delivery is on track to be completed on time.

Table 5. CoCoA-PAD Project Timeline

Milestone	Start	Finish
Submit to research ethics	June 2025	September 2025
CoCoA-PAD co-production	April 2025	November 2025
CoCoA-PAD reliability assessment	October 2025	November 2025
Finalise MRI sequence and pipeline	October 2025	November 2025
Finalise Statistical Plan	October 2025	November 2025
CoCoA-PAD pilot	November 2025	December 2025
Finalise REDCap Database	October 2025	December 2025
Publish protocol and analysis plan	November 2025	January 2026
Train staff at research sites	December 2025	February 2026
Data Collection (Study 1 & 2)	February 2026	May 2027
Send plasma to UCL Biomarker Factory	May 2027	May 2027
Launch Study 3 data collection	June 2027	December 2027
Finalise database for Study 1 & 2	June 2027	August 2027
Data analysis for Study 1 & 2	August 2027	January 2028
Review Study 1 & 2 with statistician	January 2028	February 2028
Finalise database for Study 3	January 2028	March 2028
Coproduce dissemination strategy	January 2028	March 2028
Data analysis for Study 3	March 2028	May 2028
Review Study 3 results with statistician	May 2028	June 2028
Send participants accessible infographic	June 2028	August 2028
Project write up	February 2028	September 2028
Finalise database for publication	March 2028	September 2028
End of Project	September 2028	September 2028

9. Data Management

The CoCoA-PAD data management plan has been developed in compliance with the Data Protection Act 2018 and GDPR. All aspects of the data management plan are developed in compliance with University of Plymouth's Research Data Management Plan. A summary of the CoCoA-PAD data management plan is outlined in Figure 6, and a separate data management plan has been submitted alongside the protocol, which provides additional information.

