4.6. Bias Reducing Factors

Several different methods have been used to ensure as many confounding variables as possible are controlled for.

Sampling Procedure

- A stratified research design will be used to ensure the research sample is representative of UK demographics for ethnicity and low educational attainment, both of which are risk factors for Alzheimer's disease and frequently under-represented in research (Chan et al., 2024).
- The All-Party Parliamentary Group on Dementia (2023) report outlined that access to transport is a key barrier that prevents or delays people living in rural and coastal communities for receiving a diagnosis of dementia. To ensure people with poor transport access are not excluded from this study, this study includes the option for all participants to travel to the research sites via taxi, at no cost to the participant.
- All data collected in Study 1 and Study 2 will be collected blind to the participants AD biomarker status. The AD diagnosis will be determined after the entire Study 1 and 2 samples are collected, when the AD biomarkers will be sent to the Dementia Biomarker Factory for analysis.
- Participant diagnostic status will be determined using objective criteria based on AD biomarker status and established cut off scores for MCI on the Mini Addenbrooke's Cognitive Examination (M-ACE) note that English as a first language is an inclusion criterion for this study. This is due to the confounding impact of performing cognitive assessments in a non-native language. Subsequent research will aim to adapt the CoCoA-PAD assessment so that it can be administered and scored automatically in different languages, to minimise this source of bias in the future.

Accessibility

All participant facing documents have been coproduced by members of the PPI group, who have 'signed off' on the research poster, participant information sheet, and debrief document.

Standardisation

- The recruitment screening and assessment battery will be heavily standardised and will use an assessment script (CRF). This will ensure consistency in screening and data collection for all participants.
- The scoring of all CoCoA-PAD tests will be completed using validated automated procedures, which reduces the potential for human error.

Data Analysis

- The full analysis plan will be reviewed by a statistician and approved.
- The full analysis plan will be pre-registered on the Open Science Framework.

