The MS SharePoint audio data folder will have access-controlled sharing. This data will only be available to the CI, [name], [name], [name], [name], and [name]. The audio data will be accessed by [name], at the University of Birmingham, who are listed as a Data Processor. Given the need complexity of this analysis and the need for multiple analysis pipelines, proportional data minimisation processes will be completed, as outlined previously, and [name] will have access to the raw audio recording files. Audio data will be uploaded to a locally downloaded and run version of Whisper, OpenAI, transcription service. When run locally on a computer, Whisper AI does not upload any data onto a server, and it is GDPR compliant. A transcript of the research session will be produced. Similarly, the audio file will be analysed using code that has been fully developed by [name]. Different types of acoustic and linguistic features will be extracted using Python code that is run locally - the data will not be uploaded to any third-party server at any point. Using those extracted features, a neural network classifier will be trained. The outcome of this classifier will be manually added to the REDCap database.

Demographic and Health Information

Participant demographic and health information will be collected using the Questionnaire feature of Gorilla Experiment Builder. The research sites will be provided with a survey link, with which they can administer the questionnaires and demographic survey to participants. Demographic variables collected will include participants' years of education, socioeconomic status, and relevant health history. Clinical self-report data will be gathered using standardised screening instruments for mood, sleep, and pain.

Gorilla Experiment Builder stores raw data on secure servers, which are only accessible to the primary researcher using their unique multi-factor log-in details. Therefore, only the CI will have access to this data, irrespective of where it was collected. No direct identifiers are stored in Gorilla, and therefore the data are pseudonymised. Raw data will be downloaded onto a Microsoft Excel spreadsheet and manually extracted and transferred into the primary research database on REDCap.

Neuropsychological Assessment Data

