- Include sample manifest with participant IDs and aliquot details

8. Plasma Analysis and Sharing

- The samples will be received by the UCL Biomarker Factory, who will complete the biomarker analysis using Quanterix Simoa® ALZpath pTau 217.
- A research database with pTau217 levels and the participant ID will be created and shared with the CI via the share function on MS SharePoint, which will include multi-factor log-in procedures, access control and an expiration.

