To ensure the data can be reused by external researchers, the CoCoA-PAD database includes a comprehensive metadata structure at both the variable and project levels. Each variable is clearly defined in REDCap's data dictionary. In addition, project-level metadata will be provided alongside the dataset, including a README file explaining study aims, variable naming conventions, missing data codes, and scoring instructions, and a metadata guide mapping variable to clinical constructs and study timepoints. This approach ensures that de-identified data shared with external teams will be accompanied by all the necessary contextual information for independent analysis, promoting transparency, reproducibility, and alignment with Findable, Accessible, Interoperable, and Reusable (FAIR) data principles.

At the conclusion of data collection for the CoCoA-PAD study, the database will undergo a formal closure process to ensure data integrity, regulatory compliance, and readiness for analysis. The datasets will be reviewed by a database specialist with the Peninsula Clinical Trials Unit (PenCTU) at University of Plymouth, who will review it against best practice guidance and the procedure outlined above. Any issues identified by the database specialist will be addressed. Prior to locking the database, a structured internal audit will be conducted by the study team to verify the accuracy, completeness, and consistency of the dataset. This will involve resolving all outstanding data queries, reviewing audit trails, checking for missing or anomalous values, and confirming that data entry aligns with the study protocol and consent

requirements. Once all discrepancies have been addressed and all fields are verified, the REDCap database will be transitioned to read-only status, locking all data fields to prevent further modification. The final dataset, along with a complete version-controlled data dictionary, codebook, and audit documentation, will be exported and securely archived on the University of Plymouth's institutional repository – (Plymouth Electronic Archive and Research Library (PEARL)).

Raw Audio Data

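### Masking is promised for data collection only: as scheduled, the Chief Investigator receives pTau-217 results by participant ID before the Study 1/2 index scores are locked

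*Protocol*

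**What the plan says.** **Masking.** Protocol section 4.6 states: "All data collected in Study 1 and Study 2 will be collected blind to the participants AD biomarker status". It continues: "The AD diagnosis will be determined after the entire Study 1 and 2 samples are collected". Neither sentence mentions extraction, cleaning or lock.

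**Dates.** Table 5 in section 8.10 gives, in order, "Data Collection (Study 1 & 2) February 2026 May 2027", "Send plasma to UCL Biomarker Factory May 2027 May 2027" and "Finalise database for Study 1 & 2 June 2027 August 2027". It launches Study 3 data collection in June 2027 and starts the Study 1/2 analysis in August 2027. It has no row for receipt of the biomarker results.

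**Who holds the reference result.** Section 9.3 (plasma analysis) states: "A research database with pTau217 levels and the participant ID will be created and shared with the CI". Section 9.4 (raw blood samples) has the Chief Investigator enter the results into REDCap.

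**Who holds the index data.** Section 9.3 gives access to the raw Gorilla data to the Chief Investigator alone, whatever the site, and describes the route to the database: "Raw data will be downloaded onto a Microsoft Excel spreadsheet and manually extracted and transferred into the primary research database on REDCap". That text concerns demographic and health data, but the neuropsychological data are said to follow the same process. The processed CoCoA-PAD data are also transferred manually.

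**Cleaning.** Section 9.4 has the study team resolve queries before lock, including "checking for missing or anomalous values". The database becomes read-only only after that.

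**The concern.** In a diagnostic accuracy study, the index test should be final before anyone who can still alter it sees the reference result. Here the reference result reaches the person who extracts the index scores, and who leads the test's development, while those scores can still be queried and changed.

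This matters most for primary objective i, preclinical AD against healthy controls. Both groups have subjective decline without impairment, so pTau-217 is what separates them. Unlike the M-ACE, it is unknown to the assessor until it is released, so masking is achievable and worth keeping.

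There is also real discretion to protect. Section 7.5 allows subtests to be stopped for distress and sessions to be ended early. Section 11.1 makes the handling of missing data depend on what is found. Decisions on such records, taken with the biomarker result known, could favour the test without anyone intending it.

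**Working it through.** The document gives no figure to reproduce. The check is the order of events and who holds which data.

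**1. When do the results arrive?** Table 5 does not say, but two independent routes give the same order.

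- *Through Study 3.* Section 4.3 selects 18 healthy controls and 18 people with prodromal AD by diagnostic classification. Section 4.1 bases that classification on pTau-217 and the M-ACE. Selecting for a June 2027 launch therefore needs results at about that time.
- *Through REDCap.* The Chief Investigator enters the results into REDCap (section 9.4), and a read-only database takes no entries. Results must therefore precede lock, whenever Study 3 starts.

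**2. How long is the overlap?** If results arrive at the start of June 2027 and finalisation ends in August 2027, the overlap is June, July and August, about 3 months. This is an upper limit. Receipt is undated, and so is manual extraction, part of which could be done during collection (February 2026 to May 2027). The pre-lock audit is firmer: section 9.4 places it after data collection ends.

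**3. What can still be decided then?**

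| Step | Who | Masked by the text? |
|---|---|---|
| Administering the tests | Assessors | Yes (4.6) |
| Automated scoring | Software | Little discretion |
| Scoring of audio, clock drawing and verbal fluency | Outside universities, without linkage files | In effect yes |
| Manual transfer to REDCap | From data only the Chief Investigator can access | Not stated |
| Missing, partial or anomalous values | Study team | Not stated |

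The gap is confined to the last two rows.

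**4. How sensitive is the result?** The bias cannot be computed from the document. The leverage of a single record can, as a ceiling. Section 11.3 projects 18 preclinical participants and 36 controls. The AUC is the mean, over all 18 × 36 = 648 pairs, of whether the pair is correctly ordered. One preclinical record enters 36 pairs, so it carries 36/648 = 1/18 = 0.056 of the AUC. Re-ranking one such record can move the AUC by at most 0.056, and two by at most 2/18 = 0.111. Excluding one preclinical record that is wrongly ordered against every control multiplies the AUC by 18/17 = 1.059. An assumed AUC of 0.75 would become 0.75 × 18/17 = 0.794. These are extremes for one or two records and predict nothing about what will happen.

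**The case against.** The strongest reply has four parts.

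*There is no contradiction, and lock order may be written elsewhere.* This is partly right. A reader might infer that Table 5 breaks the promise in section 4.6. It does not: 4.6 promises blind collection, and collection ends before any result exists. A separate data management plan, not shown here, may also cover the freeze. However, the protocol itself fixes the milestone order, the recipient of the results and the person with access to the raw data. Those choices produce the overlap and can be judged as written.

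*The Chief Investigator does not score the tests.* This largely stands. A reader might infer from the unscored exports that the Chief Investigator grades them by hand. Section 4.6 says scoring is automated, and section 9.3 sends speech to one university and clock drawing and verbal fluency to another, both working on pseudonymised data. The remaining discretion lies in transfer and query resolution.

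*Changes can be traced.* This stands too. Section 9.1 provides version history and monthly exports, and section 9.4 provides a log of every modification, ten-year retention of raw files and review by a PenCTU database specialist. Section 11.1 pre-registers the missing-data procedure. It would therefore be wrong to infer that neutrality could never be examined. But traceability allows a later check; it does not mask the person deciding.

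*The dates are inferred.* For receipt and extraction this is true, and it makes three months a ceiling. It does not alter the order, because the results are entered into a database that is still open.

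**Conclusion.** The point holds in a limited form. Masking stops at collection, and the schedule puts the pTau-217 results with the Chief Investigator before the Study 1/2 index scores are locked. The same person has sole access to the Gorilla data, and the handling of partial, missing or anomalous subtest scores is not masked.

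The exposure lasts at most about three months on the Table 5 dates. It could be much shorter if scores are extracted and checked during collection. It rests on two readings: that Study 3 selection uses the pTau-217 classification, as sections 4.1 and 4.3 say, and that no undisclosed document imposes an earlier freeze.

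A reader might infer that the Study 1 accuracy estimates will be biased. The document does not support that: no bias can be computed, and the existing safeguards narrow the room for it. The change is nevertheless worth making, because it is cheap and the projected preclinical group is only 18.

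**What to change.** State in section 4.6 and Table 5 that:

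- each participant's CoCoA-PAD subtest scores and M-ACE are extracted, checked and locked in REDCap on a rolling basis during collection;
- the last records are locked and a dated export made before the pTau-217 file is released to the Chief Investigator;
- until then the statistician or the PenCTU database specialist holds the laboratory file;
- for speech the extracted features are frozen, and for externally scored tasks the raw exports, if derived scores are not ready;
- any later change to an index score is logged with a reason and examined in a sensitivity analysis on the frozen export.

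Add a Table 5 row for release of the results.

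Two apparent alternatives should be avoided. Giving the Chief Investigator only a list of IDs to invite to Study 3 would reveal biomarker status. Study 3 takes only healthy controls and prodromal AD, so a listed participant with subjective decline is biomarker-negative and a listed one with MCI is positive. The Chief Investigator also tests all Plymouth participants (section 8.6). Nor need MRI-derived data be locked by May–June 2027: up to 81 scans must pass a multi-step pipeline, and MRI plays no part in objective i.

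The cost is earlier extraction and query resolution, plus one named custodian. Waiting instead for the August 2027 lock would cost more. With an 11–15 month follow-up window, participants assessed in February 2026 already reach 15 months in May 2027, before Study 3 launches, and each month of delay loses another month of early recruits. Rolling locking keeps that effect small.
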